3.4.2 Potential Risks

Administration of poractant alfa (porcine derived surfactant, Curosurf®) in infants with bronchiolitis is well tolerated and considered safe(3). Transient minor adverse reactions associated with administration of poractant alfa for the treatment of neonatal Respiratory Distress Syndrome (RDS) include bradycardia, hypotension, endotracheal tube blockage, and oxygen desaturation. The risk of such events is minimised by tracheal toilet prior to administration of poractant alfa, as recommended in the Summary of Product Characteristics.

Small volume (2x1mL/kg) non-bronchoscopic bronchoalveolar lavage (BAL) procedure on PICU is safe and well tolerated procedure(7). In a published audit of 27 children on PICU who underwent multiple small volume BAL installations (5x1mL/kg) as part of a single routine diagnostic procedure, 7 experienced transient oxygen desaturation requiring temporary increased FiO₂. We will limit BAL sampling to a 2x1mL/kg instillation at each scheduled assessment.

Small volume (1.25mL (range 1.0 to 1.3mL)) blood sampling will be done on infants ventilated at Liverpool and Southampton PICUs and scheduled to coincide with routine blood sampling. Existing vascular access will be used when available. There is no risk of anaemia associated with this limited volume of blood sampling. The sample will be taken from an arterial line if present. If not by standard venesection.

Capillary blood gas sampling (100microliters) or arterial blood gas sampling for subject monitoring will use data from routine blood gas sampling when either is collected within a 2-hour window of a research-scheduled sample. As this is part of standard care no additional risks are expected.

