3.6.2 Secondary Outcomes/Endpoints

The secondary outcome measures for the trial (WP-A) are:

For efficacy:

- 1. duration of post-extubation non-invasive respiratory support (all forms of non-invasive ventilation: e.g. nasal CPAP and nasal high low oxygen)
- 2. duration of oxygen supplementation
- 3. number of trial interventions given (both poractant and placebo)
- 4. use of steroids to assist extubation
- 5. duration of stay on PICU and in hospital;
- 6. change over time from baseline of Ventilation Index (VI), Oxygenation Index (OI) and Oxygenation Saturation Index (OSI) while mechanically ventilated, & SpO₂/FiO₂ (SF) ratio.¹
- the score (value) of parent reported outcome measure of respiratory symptoms the "Liverpool Respiratory Symptom Questionnaire" (LRSQ) at 6m (+/-1m) and 12m (+/-1m) (20);

IRAS 220853 Page **20** of **87**

¹ VI and OI are validated physiological measurements reflecting respiratory function (gas exchange) normalised for level of respiratory support provided by MV, but require blood sampling(21). OSI is a validated physiological measurement reflecting respiratory function (gas exchange) normalised for level of respiratory support provided by MV that does not require blood sampling (41). The SF ratio is a non-invasive measure of respiratory function and can be calculated in situations where invasive blood gas monitoring and MV has ceased (22).

8. time from randomisation to meeting study criteria for readiness for Spontaneous Breathing Test

For safety:

- 1. failure to administer the intervention due to any adverse event during preparatory processes (tracheal toilet or BAL)
- 2. failure to complete administration of the intervention due to any adverse event during administration of the intervention (regardless of which arm of allocation)
- 3. incidents of 'air leak' (pneumothorax and pneumomediastinum) occurring before discharge from PICU
- 4. other adverse events and serious adverse events associated with the intervention
- 5. any need to replace the endotracheal tube
- 6. parent reported readmission to hospital (all causes) up to 90 days post randomisation
- 7. death during PICU admission
- 8. all-cause mortality at 90 days post randomisation

IRAS 220853 Page **21** of **87**

Table 1: Objectives and Outcome Measures

Objectives	Outcome Measures	Timepoint(s) of evaluation of this outcome measure (if applicable)

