10.4 Relationship to Trial Treatment

The assignment of the causality should be made by the investigator responsible for the care of the participant using the definitions in Table 3: Definitions of Causality. An AE for which the causal relationship to the study drug is assessed by the investigator as "possible", "probable" or "almost certain" is an AR.

If any doubt about the causality exists the local investigator should inform the CTRC who will notify the Chief Investigator (CI). In the case of discrepant views on causality between the investigator and others, the MHRA will be informed of both points of view.

Table 3: Definitions of Causality

Relationship	Description
Unrelated	There is no evidence of any causal relationship. N.B. An alternative cause for the AE should be given.
Unlikely	There is little evidence to suggest there is a causal relationship (e.g. the event did not occur within a reasonable time after administration of the trial medication). There is another reasonable explanation for the event (e.g. the participant's clinical condition, other concomitant treatment).
Possibly	There is some evidence to suggest a causal relationship (e.g. because the event occurs within a reasonable time after administration of the trial medication). However, the influence of other factors may have contributed to the event (e.g. the participant's clinical condition, other concomitant treatments).
Probably	There is evidence to suggest a causal relationship and the influence of other factors is unlikely.
Almost certainly	There is clear evidence to suggest a causal relationship and other possible contributing factors can be ruled out.

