10.9.1 Maintenance of Blinding

Systems for SUSAR and SAR reporting should, as far as possible, maintain blinding of individual clinicians and of trials staff involved in the day-to-day running of the trial. The medical management of participants for adverse events should be undertaken under the assumption that the patient has been given surfactant (Arm A). The safety of participants in the trial always takes priority. In each report, seriousness, causality and expectedness should be evaluated for poractant alfa unless unblinding has taken place. All instances of unblinding should be reported to the CTRC.

IRAS 220853 Page **59** of **87**

Cases that are considered serious, unexpected and possibly, probably or almost certainly related to one of the trial therapies (i.e. SUSARs) would have to be unblinded at the CTRC prior to reporting to the MHRA and REC.

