#### 20. Safety Evaluations

#### 20.1. Data sets analysed

Participants who received at least one dose of either intervention or placebo will be included in the safety analysis dataset. Results will be presented by the treatment that participants actually received, rather than that to which they were allocated.

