#### 20.2. Presentation of the data

All AEs reported by the clinical investigator will be presented, with separate tables for serious and non-serious events. Both the number of events and the number of patients experiencing each event will be provided. A third table will be presented grouping non-serious AEs by severity; participants will be counted in the most severe category experienced if they experienced more than one. Similarly, a fourth table will be presented grouping non-serious ARs by causality (where the relationship to intervention is recorded as possibly, probably or almost certainly) and participants will be counted in the highest relationship category experienced if they experienced more than one.

The above tables for serious and non-serious events will be repeated but will be further grouped by whether or not the patient received muscle relaxant prior to the administration of the intervention. Serious adverse reactions will be presented as line listings, detailing the description, seriousness, severity, expectedness, relationship to intervention and outcome.

Relationship to study drug will be assessed first assuming the participant is in the intervention arm, then assuming they are in the control arm, so as to avoid unnecessary unblinding. However, for the classification of causality only the relationship to the intervention received will be reported.

For all AE descriptions, MedDRA classifications will be used. Events will be reported using the preferred term, categorised by system organ class. Results will be presented descriptively; no formal statistical testing will be undertaken for interim reports.

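### SAP 20.2 reports each event's causality only for the treatment received, so an adverse reaction is counted on a different criterion in each arm and the counts can differ when event rates do not

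*SAP*

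**What the plan says.** SAP 20.2 sets out two steps. First, the rating: "Relationship to study drug will be assessed first assuming the participant is in the intervention arm, then assuming they are in the control arm". The stated purpose is to avoid unnecessary unblinding. Second, the reporting: "However, for the classification of causality only the relationship to the intervention received will be reported".

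The same section plans an output that depends on the reported rating: "a fourth table will be presented grouping non-serious ARs by causality". It includes events rated at least possibly related and counts each participant once, in the highest category reached. Serious adverse reactions are given as line listings that include the relationship to the intervention. SAP 20.1 fixes the grouping: "Results will be presented by the treatment that participants actually received, rather than that to which they were allocated".

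Protocol 10.4 makes the rating decide whether an event is an adverse reaction at all. Its definition begins "An AE for which the causal relationship to the study drug is assessed by the investigator as" and covers the ratings from possible upwards. Protocol 10.9.1, on keeping the blind during safety reporting, says: "In each report, seriousness, causality and expectedness should be evaluated for poractant alfa unless unblinding has taken place".

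Protocol 3.6.2 lists among its safety outcomes "other adverse events and serious adverse events associated with the intervention". SAP 9.2 does not carry this outcome over and SAP 17.5 gives it no analysis, which leaves SAP section 20 as the place where it is displayed.

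**The concern.** Rating each event under both assumptions is sound: it gives every event in both arms a judgement that does not depend on knowing the syringe content. The difficulty lies in the choice of which rating to report. Because that choice follows the treatment received, surfactant infants are judged against surfactant and air infants against air.

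The documents give a reason to expect the two ratings to differ for some events. Protocol 3.4.2 says that the transient reactions associated with poractant alfa in neonatal respiratory distress "include bradycardia, hypotension, endotracheal tube blockage, and oxygen desaturation". Protocol 8.1.1 says that tracheal toilet and lavage, done in both arms, can also cause desaturation. An assessor told to assume surfactant has the drug and the procedure as candidate causes of a desaturation. An assessor told to assume air has only the procedure and the air bolus. The sham procedure is there to keep such judgements comparable between arms, and selecting the rating by arm gives up that comparability in the one table that counts reactions by causality.

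At stake is how the drug's tolerability is read. A reader who sees more related events on surfactant would take this as evidence about the drug, when part or all of it could come from the counting rule.

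**Working it through.** The plan states no figure for this rule, so there is nothing to reproduce. The check has two parts.

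**1. Which rating counts in which arm**

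| Step | Surfactant infant | Air infant |
|---|---|---|
| Ratings made (SAP 20.2) | assuming surfactant; assuming air | assuming surfactant; assuming air |
| Rating reported (SAP 20.2) | assuming surfactant | assuming air |
| Arm shown in (SAP 20.1) | surfactant | air |
| Enters the causality table if | related, assuming surfactant | related, assuming air |

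Two identical events, given identical pairs of ratings, can therefore be treated differently. If the pair is related assuming surfactant and unrelated assuming air, the event is counted in the surfactant arm and not in the air arm.

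**2. What this does to the counts**

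Inputs:
- n = 142 per arm, from Protocol 11.3: 134/0.95 = 141.05, rounded up to 142; 2 × 142 = 284.
- p = proportion of infants with a non-serious event, taken as equal in both arms. Not in the documents; assumed 20%, with 10% and 50% as a range. One event per infant is assumed, to match participant-level counting.
- q_S and q_A = probability of at least a possible rating, assuming surfactant and assuming air. Not in the documents; assumed values below.

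Formula: expected infants with a reaction = n × p × q_S on surfactant and n × p × q_A on air. The ratio is q_S/q_A; n and p cancel.

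At p = 20%, n × p = 142 × 0.20 = 28.4 infants with an event in each arm.

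| q_S | q_A | Surfactant, SAP rule | Air, SAP rule | Ratio | Both arms, common poractant rating |
|---|---|---|---|---|---|
| 0.5 | 0.5 | 14.2 | 14.2 | 1.0 | 14.2 and 14.2 |
| 0.5 | 0.25 | 14.2 | 7.1 | 2.0 | 14.2 and 14.2 |
| 0.3 | 0.1 | 8.5 | 2.8 | 3.0 | 8.5 and 8.5 |
| 0.5 | 0.1 | 14.2 | 2.8 | 5.0 | 14.2 and 14.2 |

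With q_S = 0.5 and q_A = 0.25, p = 10% gives 7.1 versus 3.6 and p = 50% gives 35.5 versus 17.8. The ratio is 2.0 each time. The distortion is set entirely by the gap between the two ratings and vanishes when there is none. A common rating gives a ratio of 1.0 in every row.

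**The case against.** The strongest reply is that the plan already holds a comparison free of this problem. SAP 20.2 tabulates all events, serious and non-serious separately, by number of events and of patients, and adds a severity table. None of these uses causality, so identical event rates would appear as such. Air leak, tube replacement, failed administration and deaths are also compared without a relatedness rating (SAP 17.5). This stands. A reader might infer that a surfactant excess in the causality table could not be told apart from real harm or from the shared procedure; that goes too far, because the all-event tables can be set beside it. One limit applies: beyond 24 hours after the last dose, non-serious events are collected only if thought related (SAP 8.8), so the tables are free of relatedness judgements only up to that point.

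The affected output is also small: one descriptive table, with no test specified, and a listing. This stands too.

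The two ratings may largely agree. The table starts at a possible relationship, for which Protocol 10.4 gives timing after administration as its example, and timing is the same under either assumption. A reader might infer that an excess is built in. The documents support only that one can arise.

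A reader might also infer that SAP 20.2 breaches Protocol 10.9.1. That section concerns blinded reporting of individual cases and does not govern final tables produced after the codes are released. The protocol supplied is v2.0, while the SAP cites v3.0 in section 5 and v6.0 in its change control, so the current text cannot be checked.

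Finally, Protocol 10.1 defines an adverse reaction as a response to a dose of the product, and an air infant received none. This is a fair point about labelling. It does not remove the asymmetry, since the SAP presents causality for both groups according to what each received. Nor would a common rating be free of bias: Protocol 7.4 accepts that some staff will infer the allocation. It would at least put the same question in both arms.

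**Conclusion.** The point holds on the SAP text alone. Under SAP 20.1 and 20.2 together, the criterion for counting an event as an adverse reaction differs by arm. The table of non-serious reactions by causality can therefore show a surfactant excess without any difference in event rates, and the same rule decides which serious events enter the reaction listing.

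The size cannot be computed from the documents. It equals the ratio of the two relatedness probabilities: 1.0 if the ratings agree, and 2.0 to 5.0 for the unequal values assumed above. An excess on surfactant is the plausible direction, but that rests on how assessors would weigh the drug's known reactions, which the documents do not measure. The all-event, serious-event and severity tables are not affected by the reporting rule, and neither is any efficacy analysis. It is worth correcting because the remedy is cheap and these are the only SAP outputs that bear directly on events associated with the intervention.

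**What to change.** In SAP 20.2:

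- Tabulate non-serious adverse reactions by causality in both arms on the same rating, the one made assuming poractant alfa, and use this as the between-arm comparison.
- Label it as a blinded common-assumption rating, so that no reader takes an air infant to have reacted to a drug not given.
- Show the rating for the treatment actually received alongside it.
- Give both ratings in the serious adverse reaction listing.

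This is in line with the case-level rule in Protocol 10.9.1 (v2.0), though that rule does not itself require it. SAP 20.2 says both ratings are already made, so no new data are needed. The cost is SAP wording and one extra column. The downside is that some air-arm events will appear as related under an assumption that was not true, which the label explains.

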#### 21. Quality Control

To ensure quality control, an independent statistician will follow this SAP to independently program the primary analysis and safety analysis from the raw data. Any discrepancies found will be discussed with the trial statistician to resolve. No programming will be shared or shown between the statisticians. The independent statistician will also check the report against their output obtained from the statistical software.

